Power Analysis: The power analysis is informed by the ICIQ-OAB symptom score reduction observed in the BETTUR PD and BETTUR2 studies of behavioral therapy for urinary symptoms in PD. Based upon the bladder diary-derived UI frequency data (consistent measure used in both behavioral and drug trials), the effect of behavioral therapy and drug therapy to reduce UI frequency is similar. The ICIQ-OAB symptom score range is 0-16, with higher scores indicating worse symptoms. A score \geq 7 would indicate clinically significant OAB symptoms (urgency, frequency, urgency UI, nocturia) occurring on average at least *sometimes*. In our previous studies, we have observed a 2-3 point reduction in the symptom score, which represents a 12%-19% reduction from baseline^{24,64}. The minimally clinically important difference for the ICIQ-OAB is defined as a statistically significant reduction in the symptom score that is accompanied by a reduction in bother and improvement in OAB-specific QOL. Because the observed reduction **\geq 2 points** represents a statistically and clinically meaningful difference, we propose a non-inferiority margin of 15%. Thus, we will randomize 90 participants in order to complete the interventions in 80 participants, which assumes 85% power and a non-inferiority margin on the OAB symptom score of 15% at 12-weeks post-randomization. **Table 6 indicates that the proposed sample size will permit an assessment of non-inferiority within a range of potential non-inferiority margins that correspond to outcome assessments in our pilot studies.**

Standard Deviation of 12 week ICIQ-OAB Symptom Score	Margin of Non-Inferiority Between Groups at 12 weeks (Assumes OAB Symptom Score at baseline of = 8.1)				
	10%	12.5%	15%	20%	
	1.0	23	16	11	7
2.0	89	59	40	24	
3.0	198	131	88	52	

Table 7: Summary Outcome Assessments

Outcome Assessment	Baseline Visit 1/Visit 2	2 weeks Visit 3	4 weeks Visit 4	6 weeks Visit 5	8 weeks Visit 6	12 weeks Visit 7
ICIQ-OAB	X			X		X
7-day Bladder Diary (drug)	X			X		X
7-day Bladder Diary (behavioral)	X	X		X		X
7-day PFME Record (behavioral)		X				
ICIQ-OAB QOL	X			X		X
Benefit & Satisfaction				X		X
Life Space Assessment	X			X		X
Self Efficacy for Chronic Disease Management	X					X
Patient Global Symptom Control Score				X		X
Adverse Event checklist	X	X	X	X	X	X
Adherence Questionnaire		X		X		X
Neuropsychological battery	X					X
MDS-UPDRS	X					X

Data Analysis:

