Primary Outcome for Aim 1: To evaluate the impact of treatment within group, we will first use a random effects mixed model with adjustment for baseline OAB symptom severity to compare mean ICIQ-OAB symptom scores across the three time points. In order to test for non-inferiority of behavioral therapy compared to drug therapy, we will assess the difference in the mean 12-week post-randomization ICIQ-OAB symptom score between groups using a two-sample t-test, assuming a non-inferiority margin of 15% and a standard deviation of 2.0 points. The significance level of the test will be set at an α of 0.025 for a one-sided test of significance.

Secondary Outcomes: The pre-treatment and post-treatment frequency of UI based on the bladder diary will be used to calculate a percentage change for each participant ($[\text{pre-treatment frequency} - \text{post-treatment frequency}] / [\text{pre-treatment frequency}] \times 100\%$). Based on pilot study results, non-normality of the diary data is anticipated and thus the Wilcoxon rank sum test will be used for bladder diary-reported outcomes (UI, urgency, nocturia). Questionnaire-based secondary outcomes (ICIQ-OAB bother score, ICIQ-QOL, benefit and satisfaction, self-efficacy, voided volume, and the Life Space Assessment) will be assessed between groups using a t-test. Twenty-four hour voided volume measures will permit an evaluation of nocturnal urine production as a confounding factor for response to treatment among persons with nocturia. Nocturnal urine production includes the sum of all voided volumes after going to bed with the intention of sleeping and the subsequent first voided volume the next morning. Additionally, an evaluation of change in mean voided volume provides an objective measure of functional bladder capacity.

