Human Subjects Involvement and Characteristics: Men and women with PD recruited from the Atlanta, Birmingham, Richmond, and Philadelphia VAMCs as well as in the surrounding community. We propose randomizing 90 participants to either exercise-based behavioral therapy or drug therapy with Solifenacain. In order to complete the study in 80 participants, we anticipated having to screen approximately 180 PD patients to identify those with clinically significant OAB symptoms, and enroll approximately 45 participants in each group. These estimates are based on our experiences in the BETTUR PD and BETTUR2 pilot studies. In the BETTUR PD study, 33 individuals were screened to enroll 20 participants. Of the 20 participants who were enrolled, 17 completed the study demonstrating a 15% drop out rate once enrolled. To date, in the BETTUR2 study, we have screened 107 individuals to randomize 51 participants and have had 6 participants drop out (11.7% rate).

During FY16, 541 unique Veterans with PD were served by the Atlanta VA and surrounding CBOCs. For the BETTUR PD pilot, 14 of the 32 screened subjects were recruited from the Atlanta VA after mailing letters to 360 Veterans identified with a diagnosis of PD in the Metro Atlanta area in FY08. Recruitment was extended to a university-based movement disorders clinic to achieve the intended sample size of 20 enrolled subjects. For the BETTUR2 study, of the 65 persons who have undergone screening procedures thus far, 25 were Veterans and 40 were recruited from university-based movement disorders clinics in Atlanta and Birmingham in order to maximize the team's ability to recruit the intended sample size. Thus, we propose to recruit both Veterans and non-Veterans for the proposed study from the outset. The university affiliates in Atlanta (Emory), Birmingham (University of Alabama at Birmingham), Richmond (Virginia Commonwealth University), Philadelphia (University of Pennsylvania) all have active movement disorders programs, which enhance the overall resources available to the study.

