The sample size is informed by the ICIQ-OAB symptom score reduction observed in the BETTUR PD and BETTUR2 studies of behavioral therapy for urinary symptoms in PD. Based upon the bladder diary-derived UI frequency data (consistent measure used in both behavioral and drug trials), the effect of behavioral therapy and drug therapy to reduce UI frequency is similar^{24,34}. The ICIQ-OAB symptom score range is 0-16, with higher scores indicating worse symptoms. A score ≥ 7 would indicate clinically significant OAB symptoms (urgency, frequency, urgency UI, nocturia) occurring on average at least *sometimes*. In our previous studies, we have observed a 2-3 point reduction in the symptom score, which represents a 12%-19% reduction from baseline^{24,64}. The minimally clinically important difference for the ICIQ-OAB is defined as a statistically significant reduction in the symptom score that is accompanied by a reduction in bother and improvement in OAB-specific QOL. Because the observed reduction (12%-19%) represents a statistically and clinically meaningful difference, we propose a non-inferiority margin of 15%. Thus, we will randomize 90 participants in order to complete the interventions in 80 participants, which assumes 85% power and a non-inferiority margin on the OAB symptom score of 15% at 12-weeks post-randomization.

Sources of Materials: The patients involved in this study will be seen in the Atlanta and Birmingham VAMC/GRECC Continence Clinics and the Philadelphia and Richmond PADRECCs. No tissue, blood, or urine samples will be stored during the study period as part of the protocol. For purposes of this research, baseline and treatment data will be stripped of all patient identifiers and each participant will be given a unique identifier for the study. Patient records will be stored in a locked cabinet in a locked office and will be accessible only to the Principal Investigator, Interventionist, Research Coordinator, Patient Recruiter, Site PI's ([name], [name], and [name]) and co-investigators ([name], [name], [name], [name]). Computer-based records will be maintained through the Veteran's Administration Computerized Patient Record System (CPRS), a secure network with password protection.

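### The sample size delivers 85% power only at about one-sided alpha 0.05; at the specified one-sided 0.025 the primary non-inferiority test has about 77%

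*Combined protocol and SAP*

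**What the plan says.** The Data Analysis section (Primary Outcome for Aim 1) specifies a two-sample t-test on the mean 12-week ICIQ-OAB symptom score, "assuming a non-inferiority margin of 15% and a standard deviation of 2.0 points". It then gives the only alpha stated for this test: "The significance level of the test will be set at an α of 0.025 for a one-sided test of significance".

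The Power Analysis section says "we will randomize 90 participants in order to complete the interventions in 80 participants, which assumes 85% power". Its sample-size table (Table 6) converts percentage margins to points under the heading "Assumes OAB Symptom Score at baseline of = 8.1", and prints 40 for SD 2.0 and a 15% margin. That 40 is per arm, since 2 × 40 gives the 80 completers.

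The opening paragraph of Research Design and Methods also gives 85% power. So does the sample-size paragraph under Human Subjects: "which assumes 85% power and a non-inferiority margin on the OAB symptom score of 15% at 12-weeks post-randomization". Allocation is 1:1; the Human Subjects section plans to "enroll approximately 45 participants in each group". In the text available here, none of these places states the alpha used for sizing.

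**The concern.** Power, alpha, margin, SD and sample size are tied together: once four are fixed, so is the fifth. The plan states all five, and they look incompatible. Forty per arm is what this margin and SD need at one-sided 0.05, whereas the test is specified at one-sided 0.025.

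This is the test for Specific Aim 1. If its power is overstated, a failure to show non-inferiority is more likely than the plan admits, and could be misread as evidence against behavioral therapy. An unreconciled alpha also leaves room to argue for 0.05 or 0.025 after the data are seen.

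**Working it through.** **Inputs**

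- Margin: 15% × 8.1 = 1.215 points (Table 6 heading).
- SD 2.0 and one-sided alpha 0.025 (Primary Outcome for Aim 1).
- 80 completers, 40 per arm; 90 randomized, 45 per arm (Power Analysis, Human Subjects).
- True difference 0. This is an assumption: the plan says only that effects on incontinence frequency are similar.

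**Formula.** For n per arm, the non-inferiority t-test has df = 2n − 2 and noncentrality margin / (SD × √(2/n)). Power is the probability that a noncentral t variable with these parameters exceeds the one-sided critical value.

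**Design cell.** At n = 40 the noncentrality is 1.215 / (2 × √0.05) = 2.717, with df = 78.

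| One-sided alpha | Critical t | Power at 40 per arm | n per arm for 85% | n per arm for 80% |
|---|---|---|---|---|
| 0.05 | 1.665 | 85.3% | 40 | 35 |
| 0.025 | 1.991 | 76.5% | 50 | 44 |

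The plan's 40 is reproduced at 0.05 and not at 0.025. The alpha that gives exactly 85% at 40 per arm is 0.049. The normal approximation tells the same story: n = 2 × SD² × (z for alpha + z for power)² / margin² gives 39.0 at 0.05 and 48.7 at 0.025. Normal-approximation power at 40 per arm is 85.8% and 77.5%.

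**Whole table** (n per arm, 85% power, t-test)

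| SD | Source | 10% | 12.5% | 15% | 20% |
|---|---|---|---|---|---|
| 1.0 | Plan | 23 | 16 | 11 | 7 |
| | alpha 0.05 | 23 | 15 | 11 | 7 |
| | alpha 0.025 | 29 | 19 | 14 | 8 |
| 2.0 | Plan | 89 | 59 | 40 | 24 |
| | alpha 0.05 | 89 | 57 | 40 | 23 |
| | alpha 0.025 | 111 | 72 | 50 | 29 |
| 3.0 | Plan | 198 | 131 | 88 | 52 |
| | alpha 0.05 | 198 | 127 | 89 | 51 |
| | alpha 0.025 | 248 | 159 | 111 | 63 |

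The recomputed rows use unrounded margins (0.81, 1.0125, 1.215, 1.62). At 0.05, 6 of 12 cells match exactly and the rest differ by 1 to 4. With margins rounded to 0.81, 1.0, 1.22 and 1.6, all 12 match exactly. At 0.025 no cell matches under either set of margins, and every printed cell is too small. Lowering the target to 80% power at 0.025 does not help: again no cell matches, and the design cell becomes 44.

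**Sensitivity to the number analysed** (alpha 0.025, margin 1.215, SD 2.0)

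- All 45 per arm: 81.3%.
- 40 per arm: 76.5%.
- 38 per arm, from the first pilot's 15% dropout (90 × 0.85 = 76.5 in total): 74.3%.

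**What would restore 85% at 40 per arm and 0.025.** Any one of these would do: a margin of about 1.36 points (1.36 / 8.1 = 16.8%), an SD of about 1.79, or a true advantage of about 0.14 points for behavioral therapy. The plan states none of them.

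**The case against.** The strongest objection is that the plan's text never says the sizing used 0.05. That is correct. It is an inference, and the exact match of all 12 cells depends on unevenly rounded margins. The Table 6 caption is also absent from the text available here and may carry an alpha. But the shortfall does not depend on the inference: whatever alpha was used for sizing, 40 per arm does not give 85% at the alpha of the test.

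Second, 77% is a single figure for something the plan leaves open. The analysis population is not defined, and participants who stop the drug may stay in the study for data collection, so the number analysed could lie between 40 and 45 per arm. That gives 76.5% to 81.3%, still below 85%. The 74.3% figure rests on a 20-person pilot; the larger BETTUR2 study reports 11.7% dropout, close to the plan's own 10 in 90.

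Third, the mixed model adjusts for baseline and might add power. As written, it serves to evaluate change within group. The non-inferiority comparison is an unadjusted t-test, so no gain can be credited.

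Fourth, type I error is not harmed, since a test at 0.025 is valid and the stricter of the two. That stands, and it limits the problem to misstated power. The misstatement still concerns the primary test.

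**Conclusion.** The concern holds. On the plan's own inputs, the primary test at one-sided 0.025 has 76.5% power with 40 completers per arm, about 8.5 points below the stated 85%. The chance of missing non-inferiority when the treatments are truly equal is 23.5%, where the plan implies 15%.

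This rests on a margin of 1.215 points, SD 2.0, no true difference, 1:1 allocation and the unadjusted t-test. A small true disadvantage for behavioral therapy would cost more: at 0.25 points, power is about 57%. That the sizing used one-sided 0.05 is a strong inference, not a documented fact.

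**What to change.** Keep 90 participants and one-sided alpha 0.025. Restate power as about 77% (40 completers per arm, margin 1.215 points, SD 2.0, true difference 0) in Research Design and Methods, Power Analysis and the Human Subjects sample-size paragraph. Recompute Table 6 at 0.025, using the values shown above, and state its alpha, margins in points and per-arm basis.

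To recover the lost power without more patients, prespecify a baseline-adjusted comparison (ANCOVA on the 12-week score with baseline ICIQ-OAB as covariate) as the primary non-inferiority analysis. Baseline scores are already collected. The gain depends on the correlation between baseline and week 12, which the plan does not give. At 40 per arm, power is about 80% for a correlation of 0.30, 83% for 0.40, 85% for 0.45 and 87% for 0.50.

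The alternative is to enlarge the trial: 50 per arm is 100 completers, and 100 / (80/90) = 112.5, so 113 randomized. Moving the test to 0.05 would also make the figures agree, but it would double the permitted risk of a false non-inferiority claim, and I would not recommend it.

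The recommended change costs corrected text and one table. The stated power becomes less favourable.

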Self-assessed adherence to exercise or drug therapy will be assessed through questionnaires (both groups) and with exercise records or pill counts depending on group allocation. Data will be calculated as medians (and inter-quartile range), and compared using Kruskal-Wallis test for continuous variables or chi-square test (Fisher's exact when expected cell counts were <5) for categorical variables. Adverse event questionnaires will be administered at each in-clinic or phone visit after treatment allocation. The number of times a specific side effect is reported after the baseline assessment will be summed and presented as a continuous variable. Comparisons between groups of the proportion of participants reporting specific side effects will be performed by Fisher's exact test.

[Specific Aim #2 (mechanistic aim): Determine if domain-specific cognitive function impacts the response to exercise-based behavioral therapy or drug therapy for urinary symptoms.

Aim 2a: Do higher baseline motor skill learning capacity and executive function scores predict better outcomes in the exercise-based behavioral therapy versus drug therapy group?

Rationale: In spite of the potential for cognitive impairment, which occurs in up to 75% of PD patients within 10 years of diagnosis²⁹, some PD patients demonstrate evidence of neuroplasticity and benefit from learning motor skills as demonstrated through functional imaging studies^{30,31}. Understanding whether baseline domain-specific cognitive function is associated with successful implementation of behavioral therapy among adults with PD is important to understand the central control of bladder function and identify new targets to augment rehabilitation therapy in the setting of a neurodegenerative disease. While participants with significant cognitive impairment (MoCA < 18) will be excluded, this exclusion criterion will not eliminate participants with mild cognitive impairment. The range of MoCA scores among current completers of the BETTUR2 PD study (n=26) is 18 to 29 (mean=24.6 ± 2.9). Among the 11 participants randomized to behavioral therapy in the BETTUR2 PD study who had a MoCA score between 18-26 (includes the screening cutpoint for mild cognitive impairment in PD³⁷), the median reduction in weekly UI frequency eight weeks after randomization was 88% (IQR 42%-100%), suggesting that even mild cognitive impairment does not interfere with learning a behavioral therapy intervention.

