To assess the potential impact on motor symptoms, we will assess the change in the motor symptom subscale of the MDS-UPDRS (part 3 score). Similar to the cognitive testing, baseline and 12-week post-randomization assessments will be evaluated using paired t-tests to assess for change within the drug group and two-sample t-tests for difference across groups, with the behavioral therapy group serving as a control for this analysis. Previous research suggests an increase in the MDS-UPDRS part 3 score of 4.6 points is associated with clinically relevant decline in motor function⁷⁰.

Visit Schedule

Visit 1: Baseline (One phone/telehealth session and one in-person session)

Explanation of study procedures and consent to be a participant

Interview: Demographics, continence and medical history, MoCA, LSA, GDS

Physical: Height, weight, vital signs, cardiac, pulmonary, and abdominal exam, genital and rectal exam, basic neurologic exam, MDS-UPDRS, determination of post-void residual by bladder ultrasound

Laboratory Examination: Urinalysis and BMP and HgbA1c if indicated

Education: How to complete bladder diary, handout take-home questionnaires (ICIQ-OAB and OAB-QOL)

Visit 2 (Part 1) : Randomization

Interview: Collect and review 7-day bladder diary, ICIQ questionnaires

Physical: Vital signs; review laboratory results; determination of post-void residual by bladder ultrasound if not conducted at first visit;

Procedure: **Randomization (Behavioral Therapy or Drug Therapy)**

Behavioral Therapy	Drug Therapy

Visit 2 (Part 2): Behavioral Therapy Randomization
 
Procedure: Neuropsychological battery, SRTT, Pelvic floor muscle exercise training
 
Education: specific behavioral techniques for constipation, modification of fluid intake or timed voiding
	
Visit 2 (Part 2) : Drug Therapy Randomization
 
Procedure: Neuropsychological battery, SRTT
 
Education: Medication

Visit 3: Behavioral Therapy (2 weeks)
 
Interview: Review PFME record, address new problems, reinforce practice at home and verbal feedback regarding muscle control
 
Education: Urge suppression strategy, management of stress-related urine loss (if applicable)
	
Visit 3: Drug Therapy (2 weeks)
 
Interview: Medication Management, Medication Side Effects
 
Education: Medication & Bladder Diary & Forms (to return at Visit 5)

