
Visit 4: Behavioral Therapy (4 weeks)
 
Interview: Review PFME record, address new problems, offer additional manual training session if subject is not satisfied with treatment or has < 25% reduction in episodes of UI based on bladder diaries.
 
Education: Reinforce strategy and PFME
	
Visit 4: Drug Therapy (4 weeks)
 
Interview: Medication Management, Medication Side Effects
 
Education: Medication and Reminder to complete Bladder Diary

Visit 5: Behavioral Therapy (6 weeks)
 
Interview: Discuss new problems, Satisfaction & Benefit questionnaire
 
Education: Reinforce PFME and urge strategy, Bladder Diary & Forms (to return at Visit 7)
	
Visit 5: Drug Therapy (6 weeks)
 
Interview: Collect and review bladder Diary; Medication Management, Satisfaction & Benefit questionnaire
 
Education: Medication & Bladder Diary & Forms (to return at Visit 7)

Visit 6: Behavioral Therapy (8 weeks)
 
Interview: Review PFME record, address new problems, offer additional manual training session if subject is not satisfied with treatment or has < 25% reduction in episodes of UI based on bladder diaries.
 
Education: Reinforce strategy and reminder to complete diary and forms
	
Visit 6: Drug Therapy (8 weeks)
 
Interview: Medication Management & Medication Side Effects
 
Education: Medication and Reminder to complete Bladder Diary

Visit 7: Behavioral Therapy (12 weeks)
 
Interview: Collect and Review diary, collect follow-up questionnaires (ICIQ and satisfaction & benefit), administer LSA, constipation, self-efficacy and adherence questionnaires
 
Procedure: Repeat neuropsychological battery
	
Visit 7: Drug Therapy (12 weeks)
 
Interview: Collect and Review diary, collect follow-up questionnaires (ICIQ and satisfaction & benefit), administer LSA, self-efficacy, and constipation questionnaires
 
Procedure: Repeat neuropsychological battery

Human Subjects:**a. Risk to Subjects**

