- Participant study documents which are identified by the participant's unique study ID, will be scanned on a VA device behind the VA firewall and uploaded to an Atlanta VA research server that is accessible to BOSS PD study personnel from each study site who are credentialed through the VA Research service at each site.
- Only deidentified data will be entered into the Redcap database by study personnel who are credentialed through the Atlanta VA Research service.

At all visits (in-clinic and telephone) after the baseline assessment, we will incorporate a standardized side effects checklist that has been used by the Continence research team for studies involving anticholinergic bladder relaxant therapy. The most common side effects reported by persons taking solifenacina are dry mouth and constipation. The risk of acute urinary retention will be reduced by excluding those with a baseline post-

void residual of ≥ 150 mL by bladder ultrasound. All adverse events and severe adverse events will be reported to the IRB, VA ORD, and the DSMB per VA policies.

References

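### The side-effect comparison counts symptoms already present before treatment because it ignores the scheduled baseline checklist, and the Visit Schedule does not match the checklist timing given elsewhere

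*Combined protocol and SAP*

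**What the plan says.** **Analysis.** The adverse-event text in the Aim 1 Data Analysis section (after Secondary Outcomes) defines the count: "The number of times a specific side effect is reported after the baseline assessment will be summed and presented as a continuous variable". It then compares the proportion of participants reporting each specific effect between arms by Fisher's exact test. It has no new-or-worsened definition and makes no use of a baseline response.

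**Timing, general statements.** Table 7 has a row "Adverse Event checklist" marked at baseline and at weeks 2, 4, 6, 8 and 12. The row carries no arm label, although the bladder-diary and exercise-record rows do. The Data Analysis section says: "Adverse event questionnaires will be administered at each in-clinic or phone visit after treatment allocation". Human Subjects, Protection Against Risk, says: "At all visits (in-clinic and telephone) after the baseline assessment, we will incorporate a standardized side effects checklist". The Drug Intervention section also calls for a standardized checklist at every visit after randomization.

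**Timing, Visit Schedule.** The drug column has "Medication Management, Medication Side Effects" at Visits 3 and 4 and an equivalent entry at Visit 6. At Visit 5 it has "Collect and review bladder Diary; Medication Management, Satisfaction & Benefit questionnaire". The behavioral column at Visit 3 reads "Review PFME record, address new problems, reinforce practice at home and verbal feedback regarding muscle control", and its Visits 4 to 6 have similar open prompts. Neither Visit 1 nor Visit 2 lists a side-effect checklist. Visit 7 has a constipation questionnaire in both columns.

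**The concern.** Two things stand out.

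First, a participant with constipation or dry mouth before treatment is counted as having a side effect on the first later report. In the summed count, the same persistent complaint can score at each of the five visits from Visit 3 to Visit 7. The baseline checklist that would separate old symptoms from new ones is in Table 7, but the analysis does not use it.

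Second, staff working from the Visit Schedule alone would prompt drug participants about side effects at three visits and behavioral participants at none, apart from the constipation questionnaire at Visit 7. They would also not collect the baseline response. The Randomization section says participants are not blinded, so unequal prompting could feed directly into what is reported.

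Freedom from drug side effects is part of the stated rationale for behavioral therapy under Specific Aim #1. If non-inferiority is shown, this comparison will weigh heavily in the choice between treatments. A baseline response that was not collected before treatment cannot be recovered later.

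**Working it through.** The plan gives no power or expected rate for this comparison, so there is no figure of its own to reproduce. The check sets the sections side by side and then illustrates the size of the dilution.

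**1. Scheduled enquiries about side effects**

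| Source | Baseline | Visits 3–7, drug | Visits 3–7, behavioral |
|---|---|---|---|
| Table 7 | yes | 5 of 5 | 5 of 5 |
| Data Analysis; Protection Against Risk | not mentioned | 5 of 5 | 5 of 5 |
| Drug Intervention | not mentioned | 5 of 5 | not addressed |
| Visit Schedule | none listed | 3 of 5 (Visits 3, 4, 6) | 0 of 5; open prompts at Visits 3–6 |

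The Visit 7 constipation questionnaire, given to both arms, is not counted in the table.

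**2. Inputs for the illustration**
- 40 per arm: half of the 80 planned completers (Power Analysis).
- Onset on drug, q: 2/9 for dry mouth, from the solifenacin pilot under Potential Risks. The same place gives 1/9 for constipation.
- Onset on behavioral therapy: 0 (assumption).
- Pre-existing prevalence, b, equal in both arms: not in the documents, so 10% to 50% is shown (assumption).
- Every pre-existing symptom is reported again after baseline (assumption).
- Two-sided Fisher's exact test at 0.05 (level assumed). Power is found by summing binomial probabilities over all tables that reject.

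**3. Any-report analysis, as planned**

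Proportion reporting on drug = b + (1 − b)q; on behavioral therapy = b. The risk difference is therefore (1 − b)q, which shrinks as b grows.
- b = 20%: 0.20 + 0.80 × 0.222 = 0.378 against 0.200; difference 0.178.
- b = 30%: 0.30 + 0.70 × 0.222 = 0.456 against 0.300; difference 0.156.

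**4. New-onset analysis**

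Restrict to those free of the symptom at baseline: n = 40(1 − b) per arm, and compare q with 0.

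| b | Power, any report | n free per arm | Power, new onset |
|---|---|---|---|
| 10% | 53% | 36 | 84% |
| 20% | 33% | 32 | 75% |
| 30% | 23% | 28 | 61% |
| 50% | 13% | 20 | 47% |

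**5. False positives with equal asking**

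With no drug effect and the same b in both arms, the test rejects 1.7%, 2.8%, 2.8% and 3.3% of the time at b = 10%, 20%, 30% and 50%. Pre-existing symptoms do not create a spurious excess.

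**6. Sensitivity of the gain**
- Onset 30% on drug against 5% on behavioral therapy (both assumed): any-report power is 38%, 22% and 11% at b = 20%, 40% and 60%, against 68%, 56% and 31% for new onset (32, 24 and 16 per arm).
- Onset 1/9 against 0: 10% against 14% at b = 20%, and 7% against 8% at b = 30%. For an effect this small neither analysis has useful power.

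**7. If asking were unequal in practice**

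With no drug effect, and the behavioral arm capturing half of its cases (assumption), the test rejects 16% of the time at 20% background and 28% at 30%. This describes a departure from Table 7, not the plan as written.

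**The case against.** A reader might infer from the Visit Schedule that only the drug arm is asked about side effects and that no baseline checklist exists, so that the comparison is biased by plan. The documents do not support that. Table 7 marks the checklist at baseline and at every later visit with no arm label. The Data Analysis and Protection Against Risk text covers all later visits without an arm restriction. The Drug Intervention text covers drug-arm Visits 5 and 7. Nothing says that the Visit Schedule overrides these sections, and it is visibly abbreviated: it also omits the Patient Global Symptom Control score at Visit 5 and the MDS-UPDRS at Visit 7, both of which Table 7 marks. An omission there is weak evidence that an item is not done. This objection stands.

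It is also fair that randomization balances pre-existing symptoms in expectation, so equal asking yields diluted contrasts rather than false ones. The prevalences are assumptions, the 2/9 comes from nine people, and no power target was set for this comparison. The repeat-visit problem affects only the summed count, which the plan says it will present; the stated test is on proportions. Finally, no section shows that the checklist grades severity, so a worsening criterion may not be available.

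None of this answers the analysis point. The plan schedules a baseline response and then compares arms without using it.

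**Conclusion.** The analysis point holds. Counting every post-baseline report mixes existing symptoms with new ones and weakens the comparison's ability to show a real drug effect. With dry-mouth onset of 2/9 against an assumed 0 and 40 per arm, power falls from 75% to 33% at an assumed 20% prevalence, and from 61% to 23% at 30%. The gain from a new-onset definition depends on the effect size and is negligible at 1/9.

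The roughly 3% false-positive rate assumes that pre-existing complaints are reported equally in both arms after treatment starts. Constipation may depart from that, because the behavioral arm is taught constipation management; this is a further reason to refer to baseline.

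The Visit Schedule point holds only as an inconsistency. Read together, the documents intend equal asking. Unequal ascertainment is a risk in an open-label trial if staff work from the Visit Schedule alone; it is not a stated rule.

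This is a secondary safety comparison. The primary non-inferiority analysis is not affected.

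**What to change.** - **Data Analysis (adverse events):** make the between-arm comparison one of side effects new since the baseline checklist, or worsened if the checklist records severity. Keep the any-report version as supportive. State how repeat reports of one symptom enter the count.
- **Baseline:** confirm that the checklist marked at baseline in Table 7 is completed before randomization, and align the Protection Against Risk text with it.
- **Visit Schedule:** add the baseline checklist, and list the same checklist at Visits 3 to 7 in both columns.
- **Visit 5, drug column:** this entry names no side-effect item, while the Drug Intervention section makes a decision at that visit depend on reported tolerability. The two must be reconciled.

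The cost is wording, plus a checklist that Table 7 already schedules at existing visits. The statistical price is a smaller denominator for each symptom, for example 32 instead of 40 per arm at 20% prevalence.
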